**IMPACT No. 19649 STATISTICAL ANALYSIS PLAN v.2.0 13 JUL 2020**

missing	missing	missing	
---------	---------	---------	--

7.3. Interim analysis and data monitoring**Interim analysis objectives**

The main purpose of interim analyses is to assess the changes after the first course of treatment with Theraflex®. The final analysis will be performed after the end of the study which is the date when the analytical dataset is completely available.

7.4. Interim analysis scheme

It is planned to have an interim analysis/analyses after 50% of subjects (first 550 enrolled) have completed Visit 2 (V2).

Study termination

No early study termination is planned by the Protocol.

7.5. Multicenter studies

This is a multicenter study. For analysis purposes, data obtained from all study sites will be combined. Disposition data will be presented by study sites.

7.6. Multiple testing

No multiple testing is planned for the study.

8. Study data**8.1. Disposition of study subjects**

Disposition of study subjects will be presented in tables and data listings with the following results:

- The number of screened and prematurely withdrawn subjects (overall and by study sites);
- The number of subjects with violations of inclusion/exclusion criteria;
- Reasons for early study withdrawal (overall and by study sites);

CONFIDENTIAL/PROPRIETARY

Data MATRIX LLC

Project code: NIS Theraflex, Statistical Analysis Plan, v. 2.0 dd. 13/07/2020

Translated from Russian on 24/08/2020

**IMPACT No. 19649 STATISTICAL ANALYSIS PLAN v.2.0 13 JUL 2020**

- The number and percentage of subjects in analysis sets;
- The number and percentage of subjects at each scheduled visit.

8.2. Protocol deviations

Protocol deviations will be presented in a listing. Protocol deviations will not result in inclusion or exclusion of subjects from analysis sets.

8.3. Demographics and baseline data

The following characteristics will be presented in tables and listings:

- demographic characteristics (for all subjects and separately for subjects with knee/hip osteoarthritis):
 - age (full years at the time of signing the IC): an automatically computed value in the CRF¹;
 - sex;
 - race (White, Black, Asian, not reported);
- anthropometric characteristics (for all subjects and separately for subjects with knee/hip osteoarthritis):
 - height (cm);
 - body weight (kg);
 - body mass index (BMI) (kg/m²): computed value in the CRF²;
- Risk factors:
 - hereditary diseases of bones and joints (description of hereditary diseases will be presented in listings only);
 - non-genetic (excess weight, hormonal disorders, malformations of the bones and joints, joint operations);
 - exogenous risk factors (professional activity, trauma, sports);
- OA staging according to Kellgren & Lawrence;

¹ Age calculation formula: [Date of informed consent signing - Date of birth].

² BMI calculation formula: [Body weight (kg)/(Height (m))²].

CONFIDENTIAL/PROPRIETARY

Data MATRIX LLC

Project code: NIS Theraflex, Statistical Analysis Plan, v. 2.0 dd. 13/07/2020

Translated from Russian on 24/08/2020

**IMPACT No. 19649 STATISTICAL ANALYSIS PLAN v.2.0 13 JUL 2020**

Data on alcohol and tobacco use will be presented in listings only.

8.4. Concomitant diseases and medical conditions

All prior and concomitant diseases will be coded using the MedDRA dictionary (version 20.1 or later) according to the standard operating procedure of Data MATRIX LLC [4] and presented in separate tables by system organ class (SOC) and preferred term (PT).

Prior and concomitant diseases will be classified based on disease status at screening as recorded by investigators on the Medical History form in the CRF. Diseases with “Resolved” status will be considered as prior. Diseases having “Ongoing, positive dynamics”, “Ongoing, negative dynamics”, “Ongoing, no dynamics” status will be considered as concomitant.

Descriptive statistics for prior and concomitant diseases will reflect the number and percentage of patients with recorded diseases and relevant SOC and PT, as well as the number of these records. Patients with multiple diseases coded within the same SOC and PT will be counted only once within each SOC and PT. A patient may have multiple PTs within a SOC.

8.5. Prior and concomitant treatments

In accordance with the Protocol, prior treatments meeting the criteria listed below are considered to be relevant to the study indication have to be documented:

- Slow-acting drugs
 - Glucosamine
 - Chondroitin
 - Hyaluronic acid
 - Diacerein
 - Unsaponifiable matters of avocado and soya
- Pain syndrome therapy
 - Analgesics
 - NSAID
- Topical pain therapy
 - Topical NSAID

**IMPACT No. 19649 STATISTICAL ANALYSIS PLAN v.2.0 13 JUL 2020**

- Intra-articular injections
- Manual therapy
- Surgery
- Physiotherapy

Treatment of comorbid diseases (Diabetes mellitus, Hypertension, Obesity)

- Antihypertensive drugs
- Drugs for treatment of diabetes
- Anticoagulants
- Other

All treatments taken in addition to Theraflex® for any indication (initiated either before or during the study) are defined as concomitant and have to be documented.

Information on medications to be collected includes:

- Trade name or INN
- Start date, stop date/ongoing
- Dose
- Unit
- Frequency
- Application route
- Indication

All prior and concomitant medications will be coded using the WHODD dictionary (version as of SEP 2017 or later) according to the standard operating procedure of Data MATRIX LLC [4] and presented in separate tables by pharmacological subgroup (3rd level) and chemical subgroup (4th level).

All treatments taken before the study start (initiated and stopped before the study start) are defined as prior treatments. Prior and concomitant treatments will be classified based on their start and end dates recorded by investigators on the Prior/Concomitant treatment form in the CRF:

- Prior treatment refers to medications started and stopped before the first dose of the study drug.
- Concomitant treatment refers to medications started after the first dose of the study drug, but before the end of treatment.

CONFIDENTIAL/PROPRIETARY

Data MATRIX LLC

Project code: NIS Theraflex, Statistical Analysis Plan, v. 2.0 dd. 13/07/2020

Translated from Russian on 24/08/2020

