7.2. Missing data

The per protocol analysis is planned to be performed using available data only with no missing data replacement methods. The exception will be incomplete dates for separation of prior and concomitant treatments, as well as for separation of AEs occurred during the study and AEs occurred prior to the initiation of the study (incomplete dates will not be replaced with any data during classification).

Prior/concomitant therapy with missing or incomplete dates of start and end of the event

Table 7.2:1 - Classification algorithm for prior, concomitant and post-treatment therapies with missing or incomplete dates of start and end of the event

Start date	End date	Actions
Known	Known	To be considered as prior therapy, if the end date is < the start date of the study drug To be considered as concomitant therapy, if the end date is >= the start date of the study drug and the start date is <= the end of treatment To be considered as post-treatment therapy, if the end date is >= the start date of the study drug and the start date is > the end of treatment
	Partially missing	The end date should be replaced with the latest date possible (i.e. the last day of the month, if the day is unknown, or December 31, if the day and the month are unknown), then: To be considered as prior therapy, if the end date is < the start date of the study drug To be considered as concomitant therapy, if the end date is >= the start date of the study drug and the start date is <= the last administration date To be considered as post-treatment therapy, if the end date is >= the start date of the study drug and the start date is > the end of treatment
	Missing	The event should not be considered as prior, if the end date is missing To be considered as concomitant therapy, if the start date is <= the last administration date To be considered as post-treatment therapy, if the start date is > the end of treatment

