**IMPACT No. 19649 STATISTICAL ANALYSIS PLAN v.2.0 13 JUL 2020**

- Post-treatment refers to medications started after the last dose of the study drug.

In case of missing or incomplete dates of start and end of treatment, the rules specified in section 7.2 will be applied (Table 7.2:1). If it is impossible to clearly determine whether the therapy was taken before, during, or after the study treatment, such therapy is defined as concomitant.

Descriptive statistics for prior, concomitant and post-treatment therapies will reflect the number and percentage of patients with prescribed treatments and relevant pharmacological and chemical subgroups, as well as the number of these records. Patients with multiple prescribed treatments coded within the same pharmacological and chemical subgroups will be counted only once within each pharmacological and chemical subgroup. A patient may have multiple chemical subgroups within a pharmacological subgroup.

9. Primary and secondary endpoint analysis

Primary and secondary endpoint analysis will be conducted in the Full Analysis Set (FAS).

For each visit, results will be presented descriptively by subscales and changes from Visit 1 for HOOS and KOOS questionnaires separately.

The results for secondary endpoints will be presented by subgroups of patients with knee osteoarthritis, patients with hip osteoarthritis and in a combined table (three types of tables will be presented).

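### The concomitant-medication bullet in SAP 8.5 leaves out complete-date drugs begun before the first Theraflex dose and stopped on or after it, contrary to Table 7.2:1 (minor)

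*SAP*

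**What the plan says.** SAP 8.5 first gives a general definition: "All treatments taken in addition to Theraflex® for any indication (initiated either before or during the study) are defined as concomitant". Protocol 9.3.3.12 has the same content. Section 8.5 then says that classification rests on the recorded start and end dates, and lists three working rules:

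- Prior: "Prior treatment refers to medications started and stopped before the first dose of the study drug".
- Concomitant: "Concomitant treatment refers to medications started after the first dose of the study drug, but before the end of treatment".
- Post-treatment: "Post-treatment refers to medications started after the last dose of the study drug".

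Two sentences follow. One refers to the table: "In case of missing or incomplete dates of start and end of treatment, the rules specified in section 7.2 will be applied". The other makes concomitant the default, but on one condition: "If it is impossible to clearly determine whether the therapy was taken before, during, or after the study treatment".

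Table 7.2:1 in SAP 7.2 is titled for therapies with missing or incomplete dates. Even so, its first row deals with records whose start and end dates are both known. For these the rule is "To be considered as concomitant therapy, if the end date is >= the start date of the study drug", together with the condition that "the start date is <= the end of treatment".

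**The concern.** The table asks whether the drug overlapped Theraflex treatment. The 8.5 bullet asks whether it was started within that treatment. The two tests part company for any drug already in use when Theraflex began and stopped later. They also part at two boundaries: a drug started on the day of the first dose, or on the day treatment ended, meets the table's rule but not the bullet's.

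Neither sentence that follows the bullets closes the gap. The pointer to Table 7.2:1 is confined to missing or incomplete dates, and complete dates are neither. The default to concomitant is for drugs whose timing cannot be determined, and complete dates determine it.

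The result is also odd. Take an analgesic begun before Theraflex and stopped during it. If part of its start date is missing, the table makes it concomitant. If both dates are complete, the bullets give it no class.

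Describing analgesic use is a secondary objective, and analgesics and NSAIDs in use at the start and stopped during Theraflex bear on it. Two programmers working from the same SAP could produce different concomitant-medication tables from the same data.

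**Working it through.** The plan states no figure to reproduce here, so the check sets the two rules side by side.

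**Inputs.** F = first Theraflex dose. L = last dose, taken as equal to the end of treatment (an assumption, since the SAP uses both terms). s and e are the complete start and end dates of the other drug, with e not before s.

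**Rules.**
- 8.5 bullets: prior if s < F and e < F; concomitant if F < s < L; post-treatment if s > L.
- Table 7.2:1, both dates known: prior if e < F; concomitant if e ≥ F and s ≤ L; post-treatment if e ≥ F and s > L.

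**Without same-day ties.** Each date falls before F, between F and L, or after L. With e not before s, that gives 3 + 2 + 1 = 6 orderings.

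| Start | End | 8.5 bullets | Table 7.2:1 |
|---|---|---|---|
| before F | before F | prior | prior |
| before F | between | none | concomitant |
| before F | after L | none | concomitant |
| between | between | concomitant | concomitant |
| between | after L | concomitant | concomitant |
| after L | after L | post-treatment | post-treatment |

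Bullets: 1 prior, 2 concomitant, 1 post-treatment, 2 unmatched. Table: 1, 4, 1 and 0. Both unmatched orderings are concomitant under the table.

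**Illustration.** Put F at day 0 and L at day 100. A drug taken from day −30 to day 40, or from day −30 to day 150, fits no bullet and is concomitant under the table. The same holds at the boundaries, for a drug taken from day 0 to day 40 or from day 100 to day 120.

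**With same-day ties.** There are five positions (before F, on F, between, on L, after L), so 5 + 4 + 3 + 2 + 1 = 15 orderings. Unmatched by the bullets: start before F with end on or after F, 4; start on F, 4; start on L, 2; total 10. Of these 10, 8 need an exact tie with F or L, so the no-tie count of 2 of 6 is the fairer summary. The table classes all 10 as concomitant.

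**The general definition.** It covers treatments taken in addition to Theraflex, whether begun before or during the study. A drug with s < F and e ≥ F overlaps Theraflex, so it is concomitant by that sentence and by Protocol 9.3.3.12 too.

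**The case against.** The best answer is that the plan already classes these drugs. The general sentence in 8.5, Protocol 9.3.3.12 and the known-dates row of Table 7.2:1 all make them concomitant, and that row can only be about complete dates. A sensible programmer would follow these three and treat the bullet as a slip. This stands as far as intent goes. A reader might infer that the SAP as a whole leaves such drugs without a class, and the documents do not support that: the gap is in the bullets. It does not dispose of the point, because the bullets are the date-based rules that 8.5 says will be used, and the text does not say that the table overrides them when dates are complete.

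Three further readings go too far:

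- A reader might infer that the general sentence and Protocol 9.3.3.12 fail to cover some cases because they refer to the study and not to the first dose. They include treatments begun either before or during the study, so the reference point excludes nothing; what counts is use alongside Theraflex.
- A reader might infer a second mismatch from the sentence in 8.5 that counts prior treatments from study start, since Theraflex may begin up to 2 weeks before inclusion. That requires study start to mean the patient's inclusion, whereas Protocol section 6 defines start of study as FPFV. The drug in question, stopped between the first dose and Visit 1, is in any case concomitant by the general sentence.
- A reader might infer that all baseline medication would be lost. Drugs still ongoing with no end date arguably fall under the table's row for a known start and missing end, which makes them concomitant if started on or before the last administration date. What remains is mainly drugs with a recorded stop date.

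It is also fair to say that orderings are not equally likely, so 2 of 6 does not measure impact.

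**Conclusion.** The point holds as a contradiction in wording, of minor severity. For complete dates, the concomitant bullet in 8.5 conflicts with the known-dates row of Table 7.2:1. For drugs that overlap Theraflex it also conflicts with the general sentence in 8.5 and with Protocol 9.3.3.12.

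Applied as written, the bullets would drop these drugs from the 8.5 concomitant tables. Whether the ATC tables in SAP 9.2 would lose them too is open: 9.2 describes those tables as similar to the ones in 8.5 and organises them by indication, without saying whether the prior and concomitant classes are used.

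The KOOS and HOOS primary endpoints, the form-based analgesic status and the percentages taken from the end-of-observation form do not depend on this rule. The analysis is descriptive, so no test is affected. The documents give no count of drugs in use at the first dose and stopped later, so the number of affected patients cannot be computed. The ordering count rests on treating the last dose and the end of treatment as the same day.

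**What to change.** In SAP 8.5, replace the concomitant bullet with the rule from the known-dates row: end date on or after the first Theraflex dose, or ongoing, and start date on or before the end of treatment. Add a sentence that Table 7.2:1 governs all records, including those with complete dates. With the prior and post-treatment bullets unchanged, and the last dose equal to the end of treatment, the three classes then cover all 6 orderings (1 prior, 4 concomitant, 1 post-treatment) and all 15 with ties (1, 13, 1).

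Two editorial additions would help but are not essential: one term for the upper boundary, which the SAP variously calls end of treatment, last administration date and last dose, and a statement of whether the 9.2 ATC tables use these classes.

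The cost is a few SAP sentences, with no new data and no new analysis. If the tables have already been produced, the sponsor should confirm and report which rule was programmed.

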**IMPACT No. 19649 STATISTICAL ANALYSIS PLAN v.2.0 13 JUL 2020**

- Post-treatment refers to medications started after the last dose of the study drug.

In case of missing or incomplete dates of start and end of treatment, the rules specified in section 7.2 will be applied (Table 7.2:1). If it is impossible to clearly determine whether the therapy was taken before, during, or after the study treatment, such therapy is defined as concomitant.

Descriptive statistics for prior, concomitant and post-treatment therapies will reflect the number and percentage of patients with prescribed treatments and relevant pharmacological and chemical subgroups, as well as the number of these records. Patients with multiple prescribed treatments coded within the same pharmacological and chemical subgroups will be counted only once within each pharmacological and chemical subgroup. A patient may have multiple chemical subgroups within a pharmacological subgroup.

9. Primary and secondary endpoint analysis

Primary and secondary endpoint analysis will be conducted in the Full Analysis Set (FAS).

For each visit, results will be presented descriptively by subscales and changes from Visit 1 for HOOS and KOOS questionnaires separately.

The results for secondary endpoints will be presented by subgroups of patients with knee osteoarthritis, patients with hip osteoarthritis and in a combined table (three types of tables will be presented).

9.1. Primary efficacy endpoint analysis

Primary endpoints:

- Changes in pain, other symptoms, functions and knee related quality of life assessed by KOOS in patients with knee OA from the first assessment throughout the observation period
- Changes in pain, other symptoms, functions and hip related quality of life assessed by HOOS in patients with hip OA from the first assessment throughout the observation period

Results for “Pain”, “Symptoms” and “Quality of Life” KOOS subscales will be calculated as $[100 - (\text{Mean score for all subscale questions} * 100) / 4]$. In case of more than 50 % of missing answers for any sub-scale, results will be considered unknown for such sub-scale.

Table 9.1.1 will be used to determine resulting scores for the KOOS-PS Function subscale. [6] All 7 questions of this scale must be answered to determine the result for functional activity.

**IMPACT No. 19649 STATISTICAL ANALYSIS PLAN v.2.0 13 JUL 2020**

Table 9.1.1: Conversion table for total scores on the KOOS-PS questions using a scale ranging from 0 (extremely difficult) to 100 (no difficulty).

Total scores (0-28)	Resulting scores for KOOS-PS (from 0 to 100)
0	100
1	94.4
2	89.5
3	85.2
4	81.4
5	78.0
6	75.1
7	72.5
8	70.3
9	68.2
10	66.4
11	64.7
12	63.0
13	61.4
14	59.7
15	58.0
16	56.0
17	53.9
18	51.5
19	48.8
20	45.6
21	42.1

CONFIDENTIAL/PROPRIETARY

Data MATRIX LLC

Project code: NIS Theraflex, Statistical Analysis Plan, v. 2.0 dd. 13/07/2020

Translated from Russian on 24/08/2020

**IMPACT No. 19649 STATISTICAL ANALYSIS PLAN v.2.0 13 JUL 2020**

22	38.0
23	33.4
24	28.2
25	22.3
26	15.7
27	8.2
28	0.0

Results for “Pain”, “Symptoms” and “Quality of Life” HOOS subscales will be calculated in a similar manner.

For HOOS-physical short form (HOOS-PS), results will be determined based on the total scores from answers given to 5 questions of this scale using Table 9.1.2. [6] All 5 questions of this scale must be answered to determine the result for functional activity.

Table 9.1.2: Conversion table for total scores on the HOOS-PS questions using a scale ranging from 0 (extremely difficult) to 100 (no difficulty).

Total scores (0-20)	Resulting scores for HOOS-PS (from 0 to 100)
0	100
1	95.4
2	91.2
3	87.3
4	83.6
5	80.0
6	76.6
7	73.1
8	69.6
9	66.1
10	62.3
11	58.3

**IMPACT No. 19649 STATISTICAL ANALYSIS PLAN v.2.0 13 JUL 2020**

12	53.9
13	49.2
14	44.1
15	38.4
16	32.1
17	25.2
18	17.6
19	9.2
20	0.0

Endpoints will be descriptively summarized by visits (n, mean calculated using 95% CI for mean, SD, minimum, maximum, quartile, median). Individual subject data with primary endpoint results will be presented in listings.

9.2. Secondary efficacy endpoint analysis

Secondary endpoints:

- Drug utilization of Theraflex® therapy as reported by the patient to their physician:
 - frequency table with assessment of treatment duration will be presented as an assessment of the drug utilization. The results will be presented by the following categories:
 - patients treated with Theraflex® for up to 1 month inclusive: (the assessment will be performed using the collected start and end dates of treatment, this category includes patients falling under the following time period: [0 days < duration for a patient \leq 30.42 days]);
 - patients treated with Theraflex® for 1-3 months: this category includes patients falling under the following time period: [30.42 days < duration for a patient \leq 91.25 days];
 - patients treated with Theraflex® for 3-6 months: this category includes patients falling under the following time period: [91.25 days < duration for a patient \leq 182.50 days];
 - patients treated with Theraflex® for more than 6 months: this category includes patients falling under the following time period: [duration for a patient > 182.50 days];
 - frequency table with the investigator's assessment of compliance with recommendations for duration of treatment with Theraflex/Theraflex Advance (Mostly complied with/Mostly not complied with).
- Patient satisfaction measured with a Likert response scale:

**IMPACT No. 19649 STATISTICAL ANALYSIS PLAN v.2.0 13 JUL 2020**

- Frequency and shift tables based on the results of the scale assessment [*very dissatisfied, dissatisfied, neither satisfied nor dissatisfied, satisfied, very satisfied*] presented overall and separately for patients with knee and hip osteoarthritis;
- Descriptive statistics for results and changes from Visit 1 (as the Likert scale data are best described by the median, not the mean, 95% CI is additionally provided for the median).
- Use of analgesics for symptomatic treatment of osteoarthritis:
 - Data will be presented on the patient's additional analgesic treatment of pain in the target joint (no/occasionally/regularly, topical agents/systemic agents/combined treatment) at the time of starting the chondroprotector (Theraflex/Theraflex Advance), at the time of study completion, as well as the investigator's assessment of the dynamics of the analgesic treatment of pain in the target joint from the start of the chondroprotector (Theraflex/Theraflex Advance) until the patient's discontinuation from the study (not changed/increased/decreased/pain treatment was discontinued) and time until complete cessation of analgesic treatment (1 month/ 2 months/ 3 months/ 6 months/ 12 months after the start of the chondroprotector), if it was completely discontinued;
 - Tables similar to those described in section 8.5 will be presented by pharmacological subgroup (3rd level) and chemical subgroup (4th level) for various indications [Symptomatic treatment with analgesics for target joint OA/ Other medication for target joint OA related pain/ Other therapy for target joint OA];

Individual subject data will be presented in listings.

